### 3. DESCRIPTION OF DESIGN AND STUDY POPULATION

#### 3.1 OVERALL DESIGN AND PLAN

This PMS is a prospective study using a continuous investigation system. Patients with type 2 diabetes mellitus will be included in the surveillance. No specific criteria (e.g., demographics, baseline characteristics, concomitant drugs in use) are defined for patient enrolment.

[figure not shown]
Patients administered JARDIANCE® Tablets will be registered preferably within 14 days from the day of first administration. Patients will be observed for up to 156 weeks (approximately 36 months) after start of the treatment with JARDIANCE® Tablets or at premature discontinuation and dropout. Observations are made at the following time points: before first administration of JARDIANCE® Tablets (screening, this visit is defined as baseline) and 12, 26, 40, 52, 64, 78, 104, 130 and 156 weeks after the start of treatment, or at discontinuation.

There are 4 separate eCRFs for 0-12 (Book 1), 13- 52 (Book 2), 53- 104 (Book 3) and 105-156 weeks (Book 4).

[figure not shown]
At 12, 52, 104 and 156 weeks after the start of treatment or at discontinuation, data are to be transmitted immediately after entered into eCRF. In case of occurrence of any adverse events, data in corresponding observation period should be immediately entered into eCRF and transmitted.

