### 5.2 SAFETY

#### 5.2.1 Endpoint(s) of safety

Primary endpoint of this study is the number of patient with adverse drug reactions (ADRs)

The other safety endpoint is the number of patient with serious adverse events (SAEs) [REDACTED]

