6.2 IMPORTANT PROTOCOL VIOLATIONS

The following table defines the different categories of important PVs. The right-most column describes which PVs will be used to exclude patients from the different patient analysis sets. The final decision about which patients will be excluded from analysis sets will be taken during the course of the study and at report planning meetings before database lock at the latest.

Table 6.2: 1 Important protocol violations

Category/ Code	Description	Example/Comment	Method	Excluded from
A	Entrance criteria not met			
A1.1	No type 2 diabetes		Automated	Efficacy
A1.2	Patient received JARDIANCE [®] treatment before registration		Manual	All
B	Informed consent			
C	Trial medication and randomisation			
C1	Incorrect trial medication taken			
C1.1	No treatment with JARDIANCE [®]		Automated	All
E	Missing data			
E1	No baseline value	No available baseline value of HbA1c and FPG for efficacy analysis	Automated	Efficacy
G	Trial specific			
G1	Invalid registration			
G1.1	No patient visit after entry	Patient made no visit after the entry	Automated	All
G1.2	Multiple registration	Patient who were already registered in this trial or over the two trials(1245.94 and 1245.98) with another patient ID In this case, all data for the later patient will not be used.	Manual	All
G1.3	Registration rule not followed		Manual	All
G1.4	Patient started JARDIANCE [®] treatment out of registration period	Patients who started treatment after the end of registration period(31May2017) *Patients who started before contract period are not entered.	Automated	All
G1.5	Not continuous investigation		Manual	All

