6.3 PATIENT SETS ANALYSED

[figure not shown]
The following two analysis sets are defined as in NIS Protocol Section 7.3. The safety set will be the basis of all demographic, baseline and safety analyses. Efficacy analysis will be on basis of the efficacy set.

[figure not shown]
- **Safety set:**
 This patient set includes all patients who didn't have important PVs regarding safety and regulatory issues as marked "All" in [Table 6.2: 1](#).

[figure not shown]
- **Efficacy set:**
 This patient set includes all patients with JARDIANCE® in the safety set who have at least one available on-treatment HbA1c or FPG value with Type II diabetes mellitus.

[figure not shown]
Table 6.3: 1 Patient sets analysed

[figure not shown]
Class of endpoint	Patient set	
	Safety set	Efficacy set
Secondary endpoints		X
Primary endpoints, safety endpoints, demographic/baseline endpoints & treatment exposure	X	

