AE analyses will be carried out after integrating AE data from CRF and AE data from Local PV safety database (Perceive).

[figure not shown]
In addition, events coded as “no adverse event”, etc. will not be included in the AE analyses. The list of codes will be provided by Drug Safety.

[figure not shown]
Priority survey items, Important identified risk, Important potential risks and Significant ADRs

The following AEs are summarised on the basis of the Standardised MedDRA queries (SMQs) or Boehringer Ingelheim customised MedDRA query (BICMQ) by primary SOC and PT.

*:1 ADRs are also summarised.

*2: ADRs occurred in summer (the onset date is in June, July, August, or September) are also summarized.

Risk ratios with 95% confidence intervals will be shown for subgroup analyses. In case that there will be the significant difference between each factor, the frequency of patients with drug related AEs (ADRs) and with serious AEs will be summarized by primary SOC and PT. Due to the high number of exploratory subgroup analyses, it is recognised that the likelihood of chance findings is high and therefore subgroup results should be interpreted with caution.

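### The multiple-registration rule (G1.2) has no linkage step, so ADRs or follow-up recorded only under a patient's second 1245.94 ID drop out of the analysis

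*SAP*

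**What the plan says.** SAP 6.2, Table 6.2: 1, places code G1.2 (multiple registration) under invalid registration. Its trigger is: "Patient who were already registered in this trial or over the two trials(1245.94 and 1245.98) with another patient ID". Its consequence is: "In this case, all data for the later patient will not be used". Cases are found manually, and the code excludes from All.

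SAP 6.3 builds the safety set from these codes: "This patient set includes all patients who didn't have important PVs regarding safety and regulatory issues as marked" All in that table. The efficacy set is a subset of the safety set, so the later record leaves both. On timing, SAP 6.2 says: "The final decision about which patients will be excluded from analysis sets will be taken during the course of the study", with the report planning meetings before database lock as the latest point.

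Four other places bear on the point:

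- Protocol 5.2.1: "Primary endpoint of this study is the number of patient with adverse drug reactions". SAP 7.8.1 likewise counts patients and not events.
- Protocol 7.3.3 treats every event from first intake to 7 days after the last intake as treatment-emergent.
- Protocol 3.1: "Patients will be observed for up to 156 weeks (approximately 36 months) after start of the treatment", or until discontinuation or dropout.
- SAP 7.8.1: "AE analyses will be carried out after integrating AE data from CRF and AE data from Local PV safety database (Perceive").

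Neither document provides for linking the later record to the retained ID. Neither says what happens to a safety-database report filed under the discarded ID.

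**The concern.** Two IDs within 1245.94 are two records of one person. The rule rightly stops that person being counted twice, but it does so by deleting one record rather than by combining the two. The person is still analysed under the first ID. If an ADR falls in the treatment-emergent window but was entered only under the second ID, an analysed patient who had an ADR is tabulated as one who did not. If the first record stops early and the second continues, a patient observed for longer is analysed as an early dropout. The last on-treatment HbA1c or FPG value is then taken too early as well.

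The primary endpoint is a count of patients with ADRs, and Protocol 7.6 sizes the study on 3,000 three-year completers and on seeing rare ADRs at least once. A rule that can remove ADRs and follow-up but never add them is therefore worth tightening, even if it touches few people.

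**Working it through.** **1. The plan's own figure.** Protocol 7.6 gives a 95% (99%) probability of at least one case among 3,000 completers at a true incidence of 0.10% (0.16%). With P = 1 − (1 − p)^n and n = 3,000:

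- p = 0.0010: 1 − 0.9990^3000 = 0.9503
- p = 0.0016: 1 − 0.9984^3000 = 0.9918

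Both stated values reproduce. G1.2 has no figure of its own.

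**2. What the rule does to one person, compared with linking.**

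| Situation | Under G1.2 | If linked |
|---|---|---|
| Two 1245.94 IDs, same course, same content | One patient, nothing lost | Same |
| Two 1245.94 IDs, an ADR only under the second, no other ADR | One patient, no ADR | One patient, ADR |
| Two 1245.94 IDs, first record stops early, second continues on treatment | One patient, short follow-up | One patient, longer follow-up |
| First registered in 1245.98, then in 1245.94 | Patient leaves 1245.94 entirely | Not a linkage case within this study |

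In the first three rows the denominator is one patient either way. The ADR count and the follow-up under G1.2 are equal to or below those under linking, never above. In the fourth row both numerator and denominator change, so the 1245.94 incidence can move either way.

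**3. Possible size.** The documents give no number of duplicates, so the inputs here are assumptions:

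- d, the share of 3,000 patients with a discarded later ID: 0.1% to 2%
- f, the share of a patient's information held only under that ID: 0 to 1
- r, the ADR risk: 10% to 20%

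Patient-equivalents lost = 3,000 × d × f. Detection probability at 0.10% = 1 − 0.999^(3,000 − lost). Fall in the ADR proportion = r × d × f. At the extreme f = 1:

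| d | Lost | Detection probability | Fall in ADR proportion (r = 10% to 20%) |
|---|---|---|---|
| 0.1% | 3 | 0.9501 | 0.01 to 0.02 points |
| 0.5% | 15 | 0.9495 | 0.05 to 0.10 points |
| 1% | 30 | 0.9488 | 0.10 to 0.20 points |
| 2% | 60 | 0.9472 | 0.20 to 0.40 points |

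At f = 0.5 the losses and falls are halved. At f = 0 there is no effect.

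**4. At preferred-term level.** At 0.10% incidence, 3,000 × 0.001 = 3 cases are expected. If one of them were entered only under a discarded ID, a third of the expected cases would go.

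**The case against.** The strongest defence is that this is ordinary de-duplication. Protocol 7.3 already excludes invalid registrations from the safety set, G1.2 sits under that heading, and keeping the first registration does not depend on outcome. A second registration made after treatment began may also fall under A1.2 (JARDIANCE "treatment before registration"), which excludes from All, and its baseline may be on-drug. All of this stands as a reason to drop the duplicate registration and its baseline. It does not justify dropping a treatment-emergent event of a person who remains validly registered under the first ID. Linking to the first ID's start date and baseline prevents double counting equally well.

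A reader might infer something stronger: that the second record usually holds the later observation time, so that such a patient's later ADRs and follow-up are simply lost. The documents do not support this. Later means registered later, not observed later. The first ID continues for up to 156 weeks or to discontinuation. No text describes patients changing site and being registered again; with 1,300 sites this is possible, but it is conjecture. Loss needs a first record that stops early or an entry made only under the second ID.

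Three further points stand. Integration of the safety database may recover some reports, although the SAP does not say that they are reassigned. Expedited reporting of ADRs to the sponsor does not depend on G1.2. Linking also has its own difficulty, because two investigators may have entered conflicting dates, doses or causality assessments.

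**Conclusion.** The point holds as a small gap in the handling rule. Within 1245.94, G1.2 as written drops any treatment-emergent ADR or on-treatment follow-up recorded only under the second ID, for a person who stays in the safety set. Compared with linking, the error can go only one way: fewer patients with ADRs, or shorter follow-up. Where the two records cover the same course, there is no error.

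The one-way statement is limited to duplicates within 1245.94. It should not be extended to overlap with 1245.98, where a patient can leave numerator and denominator together, and where these documents do not show whether the data are analysed in the other study.

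The number affected is unknown and probably small. Under the assumed ranges above, the effect lies between nothing and 60 patient-equivalents of 3,000, detection probability at 0.10% incidence stays at or above 0.9472 (against 0.9503), and the ADR proportion falls by no more than 0.4 percentage points. The overall result would hardly move; a rare preferred term could. This is a desirable clarification and not a threat to the study's conclusions.

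**What to change.** Amend the G1.2 entry in SAP Table 6.2: 1 as follows.

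- **Duplicates within 1245.94:** keep one patient under the first ID, with that ID's start date and baseline. Link to it any ADRs and on-treatment follow-up found only under the second ID, including reports held in the safety database.
- **Overlap with 1245.98:** keep the patient in one study only. List the ADRs from a discarded 1245.94 record separately, outside the incidence tables. Putting them into those tables would add events from a patient missing from the denominator, and could count the same ADR in both studies.
- **Reporting:** give the number of multiply registered patients and the number of linked or listed events.

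The cost is a short SAP addition and manual linkage of what are probably a few records. These cases are already identified manually, and exclusions are settled before database lock. The main burden is resolving conflicting entries between the two records, so the SAP should also say how that will be done.

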6.3 PATIENT SETS ANALYSED

[figure not shown]
The following two analysis sets are defined as in NIS Protocol Section 7.3. The safety set will be the basis of all demographic, baseline and safety analyses. Efficacy analysis will be on basis of the efficacy set.

[figure not shown]
- **Safety set:**
 This patient set includes all patients who didn't have important PVs regarding safety and regulatory issues as marked "All" in [Table 6.2: 1](#).

[figure not shown]
- **Efficacy set:**
 This patient set includes all patients with JARDIANCE® in the safety set who have at least one available on-treatment HbA1c or FPG value with Type II diabetes mellitus.

[figure not shown]
Table 6.3: 1 Patient sets analysed

[figure not shown]
Class of endpoint	Patient set	
	Safety set	Efficacy set
Secondary endpoints		X
Primary endpoints, safety endpoints, demographic/baseline endpoints & treatment exposure	X	

6.5 POOLING OF CENTRES

This section is not applicable because centre is not included in the statistical model.

6.6 HANDLING OF MISSING DATA AND OUTLIERS

No imputation will be performed in efficacy and safety analyses. This rule will not apply for AEs. Missing or incomplete AE dates are imputed according to BI standards ('Handling of Missing and Incomplete AE Dates' (1)).

Missing or partial date information will be replaced according to following rules.

YEAR	MONTH	DAY	YMD	DT
"Unknown" (tick-box)			UNKNOWN	.
yyyy	Null or "Unknown"	Null	yyyy	yyyy/07/01
yyyy	mm	Null or "Unknown"	yyyymm	yyyy/mm/15

If the date of data which is collected as after treatment of JARDIANCE[®] in the CRF is before start of JARDIANCE[®], they will be set to missing. This rule is not to be applied for AEs.

Date of last JARDIANCE[®] intake:

To calculate duration of JARDIANCE[®] treatment at an interim analysis, the date is imputed with the following date according to the book number.

Book1: the first treatment date + 83 days (Week 12)

Book2: the first treatment date +363 days (Week 52)

Book3: the first treatment date +727 days (Week 104)

Book4: the first treatment date +1091 days (Week 156).

At DBL, the last date in the book is imputed.

6.7 BASELINE, TIME WINDOWS AND CALCULATED VISITS

With regard to efficacy and safety endpoints, the term "baseline" refers to the last observed measurement prior to administration of JARDIANCE[®].

Efficacy analyses will be performed based on calculated visits as shown in [Table 6.7: 1](#). If two or more data points of a patient fall into the same interval, the closest value to the planned day will be selected. If there are two observations which have the same difference in days to the planned day or if there are two observations on the same day, the first value will be used.

Table 6.7: 1 Baseline, time windows and calculated visits

Week label	Planned days	Time window (actual days on treatment)	
		Start	End
Baseline		The last observed measurement prior to or on the first administration of JARDIANCE [®]	
Week 12	84	1	133
Week 26	182	134	231
Week 40	280	232	322
Week 52	364	323	406
Week 64	448	407	497
Week 78	546	498	637
Week 104	728	638	819
Week 130	910	820	1001
Week 156	1092	1002	End of study

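### SAP 6.7 defines baseline in two ways and opens Week 12 on Day 1, so in a few patients one Day 1 value can be both baseline and on-treatment

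*SAP*

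**What the plan says.** SAP 6.7 defines baseline twice. In the running text, baseline "refers to the last observed measurement prior to administration of JARDIANCE". In the baseline row of Table 6.7: 1 it is "The last observed measurement prior to or on the first administration of JARDIANCE". Only the second includes the day of first administration.

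The next row of the table gives the label, planned day, window start and window end for the first visit: "Week 12 84 1 133". Within a window the rule is: "If two or more data points of a patient fall into the same interval, the closest value to the planned day will be selected".

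SAP 6.3 admits a patient with type 2 diabetes from the safety set to the efficacy set on "at least one available on-treatment HbA1c or FPG value". SAP 6.1 says how long after the last intake a value still counts as on treatment (7 days for HbA1c, 1 day for FPG). It does not say when the on-treatment period begins. SAP 7.5.2 then summarises the change in HbA1c and FPG from baseline to the last observation in the efficacy set.

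**The concern.** Under the table, a value dated on the day of first administration qualifies for the baseline row and also falls in the Week 12 window. If it fills both, the patient's change is 0 by construction, whatever the drug did. Such a patient could also enter the efficacy set on that value alone and carry a 0 into the last-observation endpoint. Each such 0 pulls the mean change towards zero.

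The conflict between text and table also affects who is analysed. If the text is applied by date, a Day 1 value is not baseline. A patient whose only starting values are from Day 1 then has no baseline and could be excluded from the efficacy set under violation E1 in SAP Table 6.2: 1. Under the table, the same patient has a baseline and stays in.

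**Working it through.** **Step 1. Which date is Day 1?** SAP 6.6 ties weeks to dates: "Book1: the first treatment date + 83 days (Week 12". The other books use offsets of 363, 727 and 1091 days. With study day = date − first treatment date + 1:

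- 83 + 1 = 84 (Week 12)
- 363 + 1 = 364 (Week 52)
- 727 + 1 = 728 (Week 104)
- 1091 + 1 = 1092 (Week 156)

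All four equal the planned days in Table 6.7: 1, so Day 1 is the first treatment date. The Day 1 start of the Week 12 window and the day included in the baseline row are the same day.

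**Step 2. Reproduce the table's window ends.** Midpoints of adjacent planned days:

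- (84 + 182)/2 = 133
- (182 + 280)/2 = 231
- (280 + 364)/2 = 322
- (364 + 448)/2 = 406
- (448 + 546)/2 = 497
- (546 + 728)/2 = 637
- (728 + 910)/2 = 819
- (910 + 1092)/2 = 1001

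All eight printed ends reproduce, and each later window starts the day after the previous one ends. The only overlap in the table is between baseline and Week 12, and it is one day wide.

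**Step 3. What happens to a Day 1 value?**

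| Reading | Baseline? | Eligible for Week 12? | Change if used for Week 12 |
|---|---|---|---|
| Table | Yes | Yes | Exactly 0 when the same value fills both roles |
| Text, applied by date | No | Yes | Day 1 value minus an earlier value; no change can be computed if there is no earlier value |

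For FPG the Day 1 value is pre-treatment if sampling follows Protocol 5.1.2, which places the draw before that day's tablet. For HbA1c the same section fixes no sampling time, so its order relative to the first dose is unknown.

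**Step 4. How often can it be selected?** Distance from the planned day is |day − 84|. Day 1 gives 83. Over Days 2 to 133 the largest distance is 82 (Day 2), and Day 133 gives 49. Every other day in the window therefore beats Day 1. A Day 1 value becomes the Week 12 value only if the patient has no other value of that parameter in Days 2 to 133. It becomes the last observation only if no later on-treatment value of that parameter exists. It carries a patient into the efficacy set only if there is no later on-treatment value of either parameter.

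**Step 5. Does another rule remove it?** SAP 6.6 blanks a value recorded as post-treatment only if its date "in the CRF is before start of JARDIANCE", so a value dated on the start day survives. SAP 6.1 sets no lower limit. The tie rules in SAP 6.7 do not bar a baseline value from a later window.

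**Step 6. Size.** Let f be the share of patients in a mean whose change is a structural 0, and d the mean change in the others. The reported mean is f × 0 + (1 − f) × d = (1 − f) × d. The documents give neither f nor d. Taking d = −0.70 as an assumption:

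| Assumed f | Factor (1 − f) | Reported mean |
|---|---|---|
| 0.5% | 0.995 | −0.6965 |
| 1% | 0.99 | −0.693 |
| 2% | 0.98 | −0.686 |
| 5% | 0.95 | −0.665 |

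The factor does not depend on d. The share f may differ between Week 12 and the last observation, and between HbA1c and FPG.

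**The case against.** The strongest reply is that other rules leave little for the overlap to act on.

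- The closest-value rule confines the Week 12 effect to patients with nothing else in Days 2 to 133.
- Violation G1.1 removes from all sets patients who made no visit after entry, and Protocol 7.3 likewise excludes those with no observation after enrolment.
- Protocol 6.2.3 lists laboratory tests at the end-of-trial visit, including at discontinuation, so early discontinuers should have a later value.
- The eCRF seems to separate data from before and after the start of treatment, and SAP 6.1 leaves the technical treatment set-up to an analysis data set plan that is not available here.
- Efficacy is secondary, there is no control group and no hypothesis is tested. The primary endpoint, patients with adverse drug reactions, is untouched.

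Most of this stands and is why f is probably small. It does not close the gap. Protocol 5.3.3 leaves laboratory tests to the investigator, so a later visit need not bring a later HbA1c or FPG. An FPG taken more than 1 day after the last tablet is off treatment under SAP 6.1. The SAP assigns visits by day and does not say that eCRF labels override this.

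Three stronger readings are tempting, and the documents do not support them.

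- A reader might infer a dilution of 10% or 20%. Nothing in the documents makes so large a share plausible once the closest-value rule is applied.
- A reader might infer that the repeated-measures model is biased in the same way. Protocol 7.3.2 restricts that model to observations after the first administration, and SAP 4 declares no change from the protocol, so a pre-dose Day 1 value lies outside it. The Day 1 window start fails to carry that limit through, but this is a matter of implementation.
- A reader might infer from Step 2 that Week 12 should open at the midpoint of Days 1 and 84, (1 + 84)/2 = 42.5, that is on Day 43. The SAP states no midpoint rule, and a Day 43 start would discard genuine on-treatment values from Days 2 to 42.

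**Conclusion.** The point holds in a limited form. SAP 6.7 contradicts itself on baseline, and Table 6.7: 1 followed literally lets a Day 1 value be both baseline and on-treatment. For the patients described in Step 4 the change is then exactly 0, and the mean change shrinks by the factor (1 − f).

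The overlap and the direction of the effect follow from the documents. Its size does not: f is not given, and the judgement that it is small rests on the closest-value rule, G1.1 and the end-of-trial laboratory tests. The conclusion also assumes that the unseen analysis data set plan does not already bar the double use. The by-visit and last-observation changes in HbA1c and FPG, and membership of the efficacy set, are open to the effect; the safety results are not. It is worth correcting because the mean changes are the efficacy result of a descriptive study and the correction is very cheap.

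**What to change.** Make three edits to the SAP:

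1. In SAP 6.7, use one baseline definition in both text and table: the last value on or before the day of first administration.
2. In Table 6.7: 1, start the Week 12 window on Day 2 and leave its end at Day 133.
3. Add a sentence that a value used as baseline cannot count as on-treatment for any calculated visit, for the last observation, or for membership of the efficacy set under SAP 6.3.

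The cost is one table cell, one aligned definition and one sentence. A few patients with only a Day 1 value lose a Week 12 or last-observation value, and those with no later value of either parameter leave the efficacy set. An HbA1c drawn on Day 1 after the first tablet would count as baseline; that should be stated openly. If the analysis data set plan already contains such a rule, it is enough to repeat it in the SAP.
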